10.0 EVALUATION DURING TREATMENT/INTERVENTION

10.1 Treatment visits every 2 weeks for Doxil® administration for 16 weeks. At each visit: history, physical exam, KPS, toxicity assessment, CBC, platelet count.

10.2 Tumor assessment within 2 weeks following the last dose of Doxil®, optimally between 7 and 14 days. For patients with stage IV disease (TNM) with baseline lymphadenopathy on CT scans of chest, abdomen and pelvis: repeat CT scans of chest, abdomen and pelvis. Patients with Sezary syndrome will have Sézary cell count and/or flow cytometry. Patients who have a CCR should have a biopsy to document a pathological CR. Two item self-reported pruritus questionnaire will be administered at time of tumor assessment. The details for tumor assessments at 16 and 32 weeks are described in Section 12.0 and in the Table in Appendix 3.

10.3 Cardiac Safety Monitoring

All patients will be monitored for a decrease in LVEF based on the criteria below: Baseline Left Ventricular Ejection Fraction (LVEF) determinations will be performed on all patients prior to enrollment in the trial. Patients will not be enrolled if LVEF <50%. If during treatment the LVEF falls to $\leq 45\%$, or the ejection fraction (LVEF) falls by 20% from the baseline level, Doxil® will be discontinued. The investigator

**Memorial Sloan-Kettering Cancer Center
IRB Protocol**

IRB#: 05-098 A(6)

may verify the LVEF from a MUGA by obtaining an ECHO with cardiac consultation. If there is no evidence of cardiac damage determined by ECHO the patient may continue on treatment.

MUGA or ECHO (LVEF) Schedule for all patients:

- f* Cumulative anthracycline dose of $< 350\text{mg}/\text{m}^2$: physicians discretion
- f* Cumulative anthracycline dose of $\geq 350\text{mg}/\text{m}^2$: every two cycles

10.4 Within 2 weeks of tumor assessment: history, physical exam, KPS, CBC, platelet count, total bilirubin, SGOT (AST), SGPT (ALT), creatinine, uric acid, fasting triglycerides and cholesterol, T4, TSH.

10.5 Within 2 weeks after tumor assessment begin oral Targretin® for 16 weeks.

10.6 Followup visits: at 2 weeks, 4 weeks, 8 weeks, 12 weeks, 16 weeks: history, physical examination, KPS, CBC, platelet count, total bilirubin, SGOT (AST), SGPT (ALT), creatinine, uric acid, fasting triglycerides and cholesterol, T4, TSH. Tumor assessment at 16 weeks on Targretin® including self-reported pruritus questionnaire. Imaging with CT scans of the chest, abdomen and pelvis will be repeated at 16 weeks for stage IV patients if initial lymphadenopathy was present. Patients with Sézary syndrome will also have Sézary cell counts and/or flow cytometry repeated at 16 weeks. Responding patients may continue on Targretin® until progression. Followup visits will be at least every 3 months for 5 years or until signs or symptoms of tumor progression.

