6.0 CRITERIA FOR SUBJECT ELIGIBILITY

6.1 Subject Inclusion Criteria

- Patient \geq 18 years of age.
- Cutaneous T-cell lymphoma: TNM stages IB, IIA, IIB-IV with biopsy documentation within six weeks before treatment. Repeat biopsies are not required within six weeks before treatment for patients with Sézary syndrome and objective evidence of circulating cells.
- KPS \geq 60
- Acceptable organ function: absolute neutrophil count \geq 1500/ μ L, platelet count \geq 100,000/ μ L, bilirubin \leq 1.5x upper limit of normal, creatinine \leq 1.5x upper limit of normal, SGOT (AST) and SGPT (ALT) \leq 2.5x upper limit of normal
- MUGA or 2-d echocardiogram indicating an ejection fraction of \geq 50% within 42 days prior to first dose of study drug. The method used at baseline must be used for later monitoring.
- Patients previously treated with doxorubicin or epirubicin are eligible if the total cumulative dose does not exceed 300 mg/m² for doxorubicin or 540 mg/m² for epirubicin.
- Negative pregnancy test. Effective birth control measures.
- Topical corticosteroids, with the exception of those with high potency (class 1), will be allowed for patients with erythroderma-Sézary syndrome (T4) and tumor stage (T3) with intense pruritus. Therapy with non-prescription emollients will also be allowed on study.

**Memorial Sloan-Kettering Cancer Center
IRB Protocol**

IRB#: 05-098 A(6)

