9.0 TREATMENT/INTERVENTION PLAN

Dosing/Regimen:

Doxil@Dose: 20mg/m² intravenously. Frequency: 2 weeks. Number of Cycles: 8 (16 weeks)

To minimize the risk of infusion-related reactions, the first infusion of DOXIL should be administered over 90 minutes as follows:

10 mL over 1st 10 minutes

**Memorial Sloan-Kettering Cancer Center
IRB Protocol**

IRB#: 05-098 A(6)

20mL over next 10 minutes
 40mL over next 10 minutes
 then, complete the infusion over a total of 90 minutes

Targretin® Dose: 300mg/m² orally Frequency: Daily for at least 16 weeks to be started within 2 weeks of tumor assessment (It is recommended that patients be treated prophylactically with an agent to lower triglycerides such as fenofibrate or atorvastatin)

Schema:

Doxil® every 2 weeks x 8 → response assessment → within 2 weeks of tumor assessment:
 Targretin® x 16 weeks → response assessment, CR/PR → continue Targretin® until relapse.

Dose Modification Guidelines

Patients should be carefully monitored for toxicity. Adverse events, such as palmar-plantar erythrodyesthesia (hand-foot syndrome), hematologic toxicities, and stomatitis may be managed by dose delays and adjustments. Following the first appearance of Grade 1 toxicity, patients will be prescribed topical betamethasone dipropionate (Diprolene) 0.05% gel to use twice daily on hands and feet only until signs and symptoms resolve. Following the first appearance of a Grade 2 or higher adverse event, the dosing should be adjusted or delayed as described in the following tables. Once the dose has been reduced, it should not be increased at a later time.

PALMAR – PLANTAR ERYTHRODYESTHESIA	
Toxicity Grade	Dose Adjustment
1 (mild erythema, swelling, or desquamation not interfering with daily activities)	Redose unless patient has experienced previous Grade 3 or 4 toxicity. If so, delay up to 2 weeks and decrease dose by 25%. Return to original dose interval.
2 (erythema, desquamation, or swelling interfering with, but not precluding normal physical activities; small blisters or ulcerations less than 2 cm in diameter.)	Delay dosing up to 2 weeks or until resolved to Grade 0-1. If after 2 weeks there is no resolution, Doxil® should be discontinued.

**Memorial Sloan-Kettering Cancer Center
IRB Protocol**

IRB#: 05-098 A(6)

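### Section 10.3 requires on-treatment LVEF tests from 350 mg/m² cumulative anthracycline, but Appendix 3 shows Echo/MUGA before treatment only

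*Combined protocol and SAP*

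**What the plan says.** **Section 10.3 (Cardiac Safety Monitoring)** opens with "All patients will be monitored for a decrease in LVEF based on the criteria below". It then requires a baseline LVEF for everyone and sets a discontinuation rule: if LVEF during treatment is 45% or lower, or "falls by 20% from the baseline level, Doxil® will be discontinued". Below this is a two-tier timetable headed "MUGA or ECHO (LVEF) Schedule for all patients". Under 350 mg/m² cumulative anthracycline the test is left to "physicians discretion". From 350 mg/m² it is due every two cycles.

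**Appendix 3 (Schedule of Protocol Events)** has an Echo/MUGA row with a single mark, in the pre-treatment column. No Doxil or Targretin visit is marked, and no footnote refers to the 350 mg/m² tier.

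**Section 10.1** lists the tests at each Doxil visit, and LVEF is not among them.

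**Section 6.1** admits patients already treated with an anthracycline: they are "eligible if the total cumulative dose does not exceed 300 mg/m² for doxorubicin or 540 mg/m² for epirubicin". Sections 6.1 and 8.0 also say that later monitoring must use the baseline method, without giving times.

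**Section 9.0** sets Doxil at 20 mg/m² every two weeks for eight cycles.

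**The concern.** A visit schedule is the page from which site staff commonly order tests. Here it shows no LVEF test after baseline, while the body of the protocol makes repeat tests mandatory in one group. That group is the patients with the largest prior anthracycline exposure, so a test missed through this mismatch would be missed where cumulative exposure is highest. The discontinuation rule acts on an LVEF measured during treatment. If a site follows the table alone, the rule has no scheduled measurement to act on in any patient.

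The protocol itself treats cardiac risk as material. Section 3.0 gives it as a reason for not using Doxil continuously, and section 11.1 lists it first among the Doxil toxicities. This is a multi-center trial, so sites that read different pages would also collect different cardiac data.

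**Working it through.** The plan states no figure on this point to reproduce. The check has two parts: whether the two schedules can both be followed, and which eligible patients the conflict affects.

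**1. The schedules side by side**

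| Cumulative anthracycline | Section 10.3 | Appendix 3 |
|---|---|---|
| Before treatment | LVEF required | Marked |
| Below 350 mg/m² | Physician's choice | No mark |
| 350 mg/m² or more | Every two cycles | No mark |

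The first row agrees. The second is compatible, since an optional test need not appear in the table. The third is a direct conflict.

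**2. Who reaches the third row**

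Inputs: Doxil 20 mg/m² for 8 doses (section 9.0), threshold 350 mg/m² (section 10.3), prior doxorubicin up to 300 mg/m² or epirubicin up to 540 mg/m² (section 6.1).

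Assumptions: full doses are given, and prior doxorubicin and study Doxil count milligram for milligram. Prior treatment must count in some form, because study Doxil alone (8 × 20 = 160 mg/m²) could never reach 350 and the upper tier would be empty.

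Cumulative dose after dose k = P + 20k, where P is the prior dose. The threshold is reached at the first k with 20k ≥ 350 − P.

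| Prior dose P (mg/m²) | Total after dose 8 | 350 reached at dose | Doses left |
|---|---|---|---|
| 0 | 160 | never | – |
| 180 | 340 | never | – |
| 190 | 350 | 8 | 0 |
| 210 | 370 | 7 | 1 |
| 250 | 410 | 5 | 3 |
| 270 | 430 | 4 | 4 |
| 300 | 460 | 3 | 5 |

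- Reaching 350 at all needs P ≥ 350 − 160 = 190.
- Reaching it with a dose left to stop needs P ≥ 350 − 7 × 20 = 210.
- Section 10.3 does not say when the first test falls after crossing. If it falls two cycles later (an assumption), a result before dose 8 needs crossing by dose 5, so P ≥ 350 − 5 × 20 = 250.
- At P = 300 the total is 340 before dose 3 and 360 after it. On the same assumption tests fall after doses 5 and 7. If a test is also done on crossing, they fall after doses 3, 5 and 7. Section 10.3 therefore calls for two or three tests before the last dose, and Appendix 3 shows none.

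**3. Prior epirubicin**

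Section 10.3 counts anthracycline without a conversion. For a patient at the 540 mg/m² limit:

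- Counted milligram for milligram, the patient is above 350 at entry and ends at 540 + 160 = 700.
- Scaled by the ratio of the two eligibility limits, 300/540 = 0.556 (an assumption that the documents do not make), the patient enters at 540 × 300/540 = 300, crosses at dose 3 and ends at 460.

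The smallest prior epirubicin dose that reaches the upper tier is 190 mg/m² on the first count and 190 × 540/300 = 342 mg/m² on the second.

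**The case against.** **The table may not be meant to govern.** Section 10.3 carries its own timetable and does not cite Appendix 3, whereas section 10.2 sends the reader there for tumor assessments. That a site would order from the table alone is possible, but the documents do not show it. This limits how certain the harm is; it does not remove the conflict.

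**The table is damaged in the available text.** Its footnote markers do not all match their notes: the triglyceride row carries the marker defined as biopsy. The absence of a footnote should therefore be stated with some caution. However, a single mark in any column cannot express a test every two cycles. The same table does footnote other conditional tests, such as CT for stage IV disease and Sézary counts for Sézary syndrome, and none of the legible notes concerns LVEF.

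**Few patients may be affected.** The documents do not say how many patients will enter with 190 mg/m² or more of prior anthracycline. This stands.

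**Stronger readings that do not hold.** A reader might infer that LVEF monitoring is set out in three incompatible ways, with the sentence about all patients as the first. That sentence defers to the criteria beneath it, so it introduces the two-tier timetable and does not compete with it. The conflict is between two places.

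A reader might also infer that the discontinuation rule cannot operate under section 10.3. From 350 mg/m² that section does schedule tests that can trigger it. Below 350 mg/m² a discretionary test can trigger it, and history, physical examination and toxicity assessment at every Doxil visit may prompt one. Patients who stay below 350 mg/m², including all anthracycline-naive patients, do have only discretionary testing to inform the rule. The protocol states this choice openly, and the documents give no figure showing it to be inadequate. Wanting fixed tests there is a preference about monitoring intensity.

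**Conclusion.** The concern holds as a two-way inconsistency with a safety consequence. From 350 mg/m² cumulative anthracycline, section 10.3 makes on-treatment LVEF tests mandatory and Appendix 3 omits them.

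The affected group is patients with at least 190 mg/m² of prior anthracycline. If the result is to be able to stop a remaining Doxil dose, the lower bound is 210 mg/m², or 250 mg/m² if the first test comes two cycles after crossing. At the doxorubicin entry limit, five of the eight doses follow the crossing. The size of the group among the 37 planned patients cannot be derived from the documents.

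These bounds assume full Doxil doses and milligram-for-milligram counting of prior doxorubicin. Dose reductions would raise them. For epirubicin they depend on a counting rule that the protocol does not state; this is a secondary clarification. Nothing here shows that discretionary testing below 350 mg/m² is an error.

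**What to change.** Reconcile section 10.3 and Appendix 3 so that both show the same LVEF schedule, including any conditional on-treatment entry and a footnote that states its condition. In section 10.3, state how prior epirubicin counts toward the 350 mg/m² threshold. The investigators decide which schedule applies; no monitoring or stopping rule is proposed here.

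The cost is an amendment to one table and one paragraph. If the current text of section 10.3 is kept, Appendix 3 would only be brought into line with it, and no test beyond those already required would be added.

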12.0 CRITERIA FOR THERAPEUTIC RESPONSE/OUTCOME ASSESSMENT

- 12.1 At 16 weeks (completion of Doxil® treatment) and after 16 weeks of Targretin® treatment: CT scans of chest, abdomen and pelvis for TNM stage IV patients who had positive findings prior to treatment.

**Memorial Sloan-Kettering Cancer Center
IRB Protocol**

IRB#: 05-098 A(6)

- 12.2 History and physical examination including skin assessment
- 12.3 Karnofsky performance status.
- 12.4 CBC with Sézary cell count and/or flow cytometry in patients with Sézary syndrome.
- 12.5 Assessment of response status and any residual toxicity will be performed 4 weeks after completion of treatment.
- 12.6 Biopsy of residual lesions 4 weeks after the completion of treatment if clinical complete remission is suspected.
- 12.7 Dermatologic evaluation of response

Dermatologic responses will be determined by the Severity-Weighted Assessment Tool (SWAT), a standardized approach to measuring the extent and severity of overall skin disease in patients with CTCL. It will be briefly described and full details are provided in an appendix. The purpose of this description is to optimize intra-observer objectivity and to minimize the potential for intra-observer and inter-observer variability in the measurement of overall skin disease. Only physicians who received training will be permitted to conduct SWAT assessments during the clinical study. It is essential that physicians adhere as closely as possible to the prescribed procedures so as to reduce measurement error and variability. All efficacy assessments should be performed by the same physician for each patient whenever possible. Physicians will be instructed not to examine previous SWAT assessments and full body photographs prior to conducting the current SWAT assessment.

1. Total Body Surface Area (TBSA) Involvement by Skin Disease

The body is divided into 12 regions with pre-assigned %TBSA based on the burn literature. The extent of skin disease in each region is quantified by using the patient's palm to measure the %TBSA involvement within region:
Patient's palm with 4 fingers (excluding the thumb) is 1% of TBSA
Patient's palm without fingers is 0.5% of TBSA.

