Responses will be determined by the criteria described in the table below. Progression of disease while on treatment should be confirmed by a second assessment 1-4 weeks later so that patients who experience a temporary flare of disease due to skin infection or other intercurrent illnesses are not removed from the study prematurely.

Assessment	Description	Status
Completely clear	No evidence of disease; 100% improvement	CCR
Marked Improvement	Greater than or equal to 50% decrease in skin scores compared to baseline and improvement is maintained for 4 weeks	PR
Slight Improvement	Less than 50% decrease in skin scores compared to baseline	SD
Worse	$\geq 25\%$ increase in skin scores compared to baseline while the patient is actively taking the study drug or $\geq 50\%$ increase in the sum of the products of the greatest diameters of pathologically positive lymph nodes (should be documented by biopsy) compared to baseline while the patient is actively taking the study drug.	PD

Assessment of Overall Skin Disease

Pruritus Relief (Appendix 1)

The intensity of pruritus will be evaluated by the patient at baseline, at the week 16 (end of treatment with Doxil®) and week 32 (after 16 weeks of treatment with Targretin®) using a 1-10 point scale, where 0 is no pruritus and 10 is the worst imaginable pruritus. A 3-point decrease in pruritus intensity confirmed by a second assessment at least 4 weeks later without an increase in the use of anti-pruritic medications is considered clinically significant in those whose pruritus score is ≥ 3 on the 0-10 point scale at baseline.

4. As a secondary goal, index lesion severity will be evaluated by a modified Composite Assessment Scale (Appendix 2). These are measurements of skin disease that have been employed and validated in the phase II-III studies of Targretin® and in the current MSKCC trial of Targretin® of Intron-A® (IRB #01-128) in CTCL. Up to 4 index skin lesions will be chosen from representative patch, plaque and tumor lesions, and erythrodermic lesions. For erythrodermic patients, a 10x10 cm. area, easily identified by anatomic landmarks will be chosen and assessed by the same scale. These index lesions will be photographed and assessed at the same time as the SWAT assessment.

In the Phase II-III studies of Targretin capsules in CTCL, the Composite Assessment (CA) of Index Lesion Disease Severity was based on a core element of the summation of index lesion

**Memorial Sloan-Kettering Cancer Center
IRB Protocol**

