14.0 BIOSTATISTICS

This is a phase II, multi-center, open-label, single arm trial. The goal of this trial is to improve response rate and prolong progression-free survival in patients with cutaneous T-cell lymphomas with the sequential use of Targretin® after an optimal course of Doxil®. The primary endpoint is progression-free survival at 12 months. Based on historical data, the median progression-free is 12 months for treatment of CTCL with Doxil®. With the new treatment, this trial will be considered as promising if the probability of progression-free at 12 months is 70%. Thirty seven patients are needed in this trial with conventional type I error 0.05 and power 0.8. This trial would be considered to be promising for further study if 24 or more patients are progression free at one year. There is 80% chance of observing 24 or more progression-free out of 37 patients if the true rate is 70% or better.

**Memorial Sloan-Kettering Cancer Center
IRB Protocol**

IRB#: 05-098 A(6)

The second endpoints are complete response and partial response rates.

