Appendix 3: Schedule of Protocol Events																
Week	PreRx	W .2	W .4	W .6	W .8	W .10	W .12	W .14	W .14-16	W .14-16	W .16-18	W .18-20	W .22-24	W .26-28	W .30-32	
	Rx Dose 1	Dose 2	Dose 3	Dose 4	Dose 5	Dose 6	Dose 7	Dose 8		Rx Day 1	Rx W .2	Rx W .4	Rx W .8	Rx W .12	Rx W .16	
Resp. Eval.									X						X	
Rx	Do xil	Do xil	Do xil	Do xil	Do xil	Do xil	Do xil	Do xil		Targ retin	Targ retin	Targ retin	Targ retin	Targ retin	Targ retin	
Hx/Px	X	X	X	X	X	X	X	X	X	X	X	X	X	X	X	
KPS	X	X	X	X	X	X	X	X	X	X	X	X	X	X	X	
Toxicity assess.		X	X	X	X	X	X	X	X	X	X	X	X	X	X	
Tumor measurements	X								X***						X***	
Skin score																
Pruritus questionnaire	X								X						X	
CBC	X	X	X	X	X	X	X	X	X	X	X	X	X	X	X	
Fasting: Trigl.*** Cholest.	X								X		X	X	X	X	X	
Lytes, BUN, Cr., AST, ALT, alk. phos., bili., TP, alb., Ca, amylase, UA, gluc	X								X		X	X	X	X	X	
Urinal.	X															
T4, TSH	X								X		X	X	X	X	X	
Echo/MUGA	X															
CT c/a/p*	X								X						X	
Sézary cell CT/Flow	**** X								X						X	
beta-HCG**	X								X							
*Pts. with stage IV (TNM)																
**premenopausal women within 7 days																
***biopsy of residual lesions if CCR																
****fasting triglyc. obtained at each MD visit																
*****Pts. with Sézary syndrome																

Schedule of Protocol Events

**Memorial Sloan-Kettering Cancer Center
IRB Protocol**

IRB#: 05-098 A(6)

Appendix 4

DATA COLLECTION FORM SCHEDULE

FORM	BASELINE	CYCLE	OFFSTUDY	WHEN APPLICABLE
Demographic, Disease & Prior Treatment Form	X			
Comorbidity Form	X			
Original Pathology Reports*	X			
Original Radiology Reports	X			
Treatment & Treatment Modification Form		X	X	
Physical Exam Form		X	X	
Laboratory Form	X			
Toxicity Form		X	X	
Concomitant Drug Form	X	X	X	
Hospitalization Form				X
Patient Status & Outcome Form				X

* Pathology report must be faxed to the MSKCC Clinical Trials Office [contact] at the same time as patient registration that confirms patient has Cutaneous T-Cell Lymphoma.

Schedule:

Baseline: Forms to be submitted within two weeks of registration.

Cycle: To be completed after each cycle and submitted every 4 weeks.

Off-study: To be submitted within four weeks of the protocol completion.

Please submit forms to:

**[name], Research Study Assistant
Memorial Sloan-Kettering Cancer Center
[name]
[name]
[contact]**

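### The go/no-go count is read at one year, but no tumor measurement is required after about week 32 and the progression criteria stop applying when study drug stops

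*Combined protocol and SAP*

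**What the plan says.** Section 14.0 names progression-free survival at 12 months as the primary endpoint and gives one decision rule: "This trial would be considered to be promising for further study if 24 or more patients are progression free at one year". It states no start date for the 12 months, no assessment window, and no rule for a patient whose status at that time is unknown.

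Tumor assessments are dated in three places, which agree:
- Section 10.2: "The details for tumor assessments at 16 and 32 weeks are described in Section 12.0 and in the Table in Appendix 3".
- Section 10.6, for the second of these: "Tumor assessment at 16 weeks on Targretin® including self-reported pruritus questionnaire".
- Appendix 3, whose last column is weeks 30 to 32, counted from the first Doxil dose.

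Section 12.5 adds one assessment tied to the end of treatment, not to the calendar: "Assessment of response status and any residual toxicity will be performed 4 weeks after completion of treatment". Later contact is set by Section 10.6: "Followup visits will be at least every 3 months for 5 years or until signs or symptoms of tumor progression". No skin score, CT or Sézary count is named for those visits.

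The PD row of the response table in Section 12.7 has two limbs. The skin limb is a rise of at least 25%, worded as an "increase in skin scores compared to baseline while the patient is actively taking the study drug". The nodal limb is a rise of at least 50% in "pathologically positive lymph nodes (should be documented by biopsy) compared to baseline while the patient is actively taking the study drug". The text above the table asks that progression on treatment be confirmed by a second assessment 1 to 4 weeks later.

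Sections 4.2 and 10.6 allow responders to stay on Targretin until relapse or progression. They do not say what patients with stable disease do after 16 weeks. Sections 5.0 and 13.0 take patients with unacceptable toxicity off study. Section 9.0 does the same for dose-limiting toxicity at the lowest Targretin dose level.

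**The concern.** The trial's only decision rests on a count at one time point, and no required procedure produces that count. A site could follow the plan exactly and record no skin score after about week 32, some 20 weeks before month 12. Two sites could also classify the same course differently, because the plan does not say whether status comes from the last visit before month 12 or the first one after it.

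For patients off drug the gap is also one of definition. Worsening after study drug stops meets neither limb of the PD row. Section 10.6 mentions signs or symptoms of progression but does not define them, so off-drug worsening need not count as progression.

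The stake is the 24/37 conclusion itself. The missing conventions would have to be chosen once data are in hand, and a skin score not taken around month 12 cannot be recovered.

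**Working it through.** **1. The plan's own figure.** Inputs from Section 14.0: n = 37, success if X ≥ 24, p1 = 0.70, and p0 = 0.50 as implied by a 12-month median. With X binomial:
- P(X ≥ 24 | 37, 0.50) = 0.0494
- P(X ≥ 24 | 37, 0.70) = 0.8071

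The stated 0.05 and 80% reproduce as a one-sided exact test. The sample size is not at fault.

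**2. Where measurements fall.** Twelve months is 365.25/7 = 52.18 weeks. The last dated assessment is at about week 32, so the gap is 52.18 − 32 ≈ 20 weeks. For a patient who stops after 16 weeks of Targretin (weeks 30 to 32), the Section 12.5 assessment falls at about weeks 34 to 36. For a later stopper it may happen to fall near month 12, but it is not tied to it. Visits 13 weeks apart from week 32 fall at weeks 45 and 58. Section 10.6 equally permits weeks 39 and 52.

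**3. Who has a criterion at month 12.**

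| Patient at month 12 | PD criterion | Dated measurement |
|---|---|---|
| Still on Targretin | Yes (Section 12.7) | No |
| Off drug, no progression so far | None stated | No |
| Taken off study for toxicity | None stated | No; continued follow-up not stated |

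**4. Effect of when status is read (illustration).** Assume exponential progression-free survival through the plan's rates: S0(w) = 0.5^(w/52.18) and S1(w) = 0.7^(w/52.18). Assume also that all patients share one visit pattern and that progression is recognised at each visit.

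| Status in effect read at | S0 | S1 | Type I error | Power |
|---|---|---|---|---|
| Week 45 | 0.5500 | 0.7352 | 0.149 | 0.913 |
| Week 52 | 0.5012 | 0.7009 | 0.051 | 0.810 |
| Week 58 | 0.4628 | 0.6727 | 0.018 | 0.692 |

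The week-45 row applies if progression first seen at week 58 is dated to its detection, so that the patient counts as progression free at month 12. The week-58 row applies if that patient counts as a month-12 failure. The plan states neither convention.

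With a Weibull curve, S(w) = p^((w/52.18)^k), where p is the 12-month rate, and shape k from 0.7 to 1.5, type I error runs from 0.111 to 0.227 at week 45 and from 0.025 to 0.010 at week 58. The direction holds; the size does not.

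**5. Effect of unknown status, with no curve assumed.** Let m of 37 patients have unknown status, unrelated to outcome.
- Counted as failures: power = P(X ≥ 24 | 37 − m, 0.70). For m = 1, 2, 3, 4 this is 0.737, 0.652, 0.555, 0.450.
- Counted as progression free: type I error = P(X ≥ 24 − m | 37 − m, 0.50). For m = 1, 2, 3, 4 this is 0.066, 0.088, 0.115, 0.148.

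The documents give no basis for any value of m.

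**The case against.** The best defence is that measurement is not absent. Visits at least quarterly are required for 5 years, and they end at signs or symptoms of progression, so detecting progression is part of their purpose. For patients on drug, PD is defined by skin score and must be confirmed, and Section 13.0 acts on progression whenever it occurs. Applying those rules after week 32 implies scoring when progression is suspected. This stands for patients on Targretin: what they lack is a dated, explicit assessment.

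A second objection is that the error rates depend on chosen visit dates, dating conventions and missing counts. This also stands. A visit at week 52 is allowed and gives 0.051 and 0.810, almost the nominal design. The 50% null rate is itself only implied: Section 14.0 cites a 12-month median, while Section 3.0 reports an event-free survival of 12.0 ± 9.5 months without calling it a median.

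A reader might infer that the trial's true type I error is about 0.15, that progression after week 32 would go undetected, or that the sample size is wrong. The documents support none of these. They fix no visit at week 45, they do require follow-up visits, and 37 with a cutoff of 24 is correct for the stated rates.

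Neither objection supplies a required score at month 12, a criterion for patients off drug, or a rule for unknown status.

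**Conclusion.** The point holds, and it should be settled before the 24/37 count is relied on. It is a gap in ascertainment and definition, established by the text alone: no tumor assessment is dated beyond about week 32, no skin score is required at later visits, both PD limbs are confined to time on study drug, and the decision is taken at one year.

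Its size cannot be measured from the documents. Under the stated assumptions, type I error could lie between 0.018 and 0.149, and power between 0.692 and 0.913, depending on whether status is in effect read at week 58 or week 45. Two unknown statuses would bring power to 0.652 if counted as failures, or type I error to 0.088 if counted as progression free. These figures show how sensitive the rule is; they do not estimate what the trial's error rates are. The number of patients off drug before month 12 is unknown, and no figure here isolates them.

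**What to change.** - **Section 10.6 and Appendix 3:** require SWAT at the follow-up visits already planned through month 12. Aim one at week 52 (for example ±2 weeks) from first Doxil dose. Scoring beyond month 12 is not needed for this endpoint.
- **Section 12.7:** state that, for the progression-free survival endpoint, the same skin and nodal thresholds apply after study drug stops. Progression confirmed at the 1 to 4 week repeat is dated to the first assessment. Month-12 nodal status uses examination and any imaging already obtained, with no added CT or biopsy.
- **Sections 5.0, 9.0 and 13.0:** reconcile the wording that takes patients off study with endpoint follow-up, so that those who leave treatment without progression are still followed for month-12 status. Treatment rules are unchanged.
- **Section 14.0:** state first Doxil dose as the start of the 12 months. Count unknown month-12 status as not progression free in the 24/37 rule, report the number, and add a sensitivity analysis.

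The sample size and cutoff stay as they are. The cost is an amendment, a little scoring time by physicians already trained in SWAT, and follow-up of patients who stop treatment. Counting unknowns as failures does not raise type I error but loses power as in step 5, so missing statuses should be kept few. The window also has a price: under the exponential illustration, seeing every patient at week 50 gives 0.071 and 0.844, and at week 54 gives 0.036 and 0.773. Visits should therefore be aimed at its centre. Nodal progression that neither examination nor existing imaging shows would still be missed.
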